#### 15.2.4.2 Immune-Related Adverse Events

Immune-related adverse events (irAEs) will be identified programmatically. AEs which satisfy all of the following criteria will be flagged as immune-related:

- 1) The AE preferred term matches a preferred term on the list of pre-selected MedDRA terms.
- 2) The AE onset or worsening occurs after the first study drug administration and no more than 90 days after last dose.
- 3) On the “AE” eCRF page, the question “Were Corticosteroids, Immunosuppressants, or hormonal therapy (e.g. Thyroid) applied?” has the answer “Yes” selected.
- 4) On the “imAE SPECIFIC QUESTIONS” eCRF page, either:

a. The question “Does any of the following provide a clear etiology for the event?” has the answer “No” selected, indicating that the AE is not attributable to underlying cancer disease/PD, prior or concomitant medications/procedures, nor another medical condition such as an infection or pre-existing disease.

OR

b. The “imAE SPECIFIC QUESTIONS” eCRF page indicates that a biopsy was performed and the question “Is the histopathology/biopsy consistent with an immune-mediated event?” has the answer “Yes” selected.

In the case that criteria (1) through (3) are met, and entries for condition (4) are missing, the following rules will be applied:

- If the answer to “Does any of the following provide a clear etiology for the event?” (4a) is missing, the event will be considered as irAE (irrespective of biopsy results).
- If the answer to “Is the histopathology/biopsy consistent with an immune-mediated event?” (4b) is missing, or if no biopsy was performed, and condition (4a) is not satisfied, i.e. “Yes” is selected (i.e. at least one (clear) etiology of the event is provided) as the answer to the question “Does any of the following provide a clear etiology for the event?”, the event will be considered as a non-irAE.

All non-pre-treatment AE records will be flagged for an event if at least one non-pre-treatment record satisfies the criteria.

PTs will be compiled into categories: Immune-mediated rash, Immune-mediated colitis, Immune-mediated pneumonitis, Immune-mediated hepatitis, Immune-mediated nephritis and renal dysfunction, Immune-mediated endocrinopathies (Adrenal insufficiency, Hypogonadism, Pituitary dysfunction, Type 1 Diabetes Mellitus, Thyroid disorders), Other immune-mediated adverse events (myositis, myocarditis, pancreatitis, neurologic events, other).

Immune-related adverse events (irAEs) will be summarized by the following variables:

- Any irAEs
- irAEs by the worst grade
- irAEs leading to permanent treatment discontinuation
- Serious irAEs

The frequency table of immune-related AEs by worst grade, category, subcategory (for Immune-mediated endocrinopathies), sub-subcategory (for Immune-mediated endocrinopathies – thyroid disorders) and PT will also be provided.

The listing of irAE will also be provided with the relevant information, including additional interventions for irAE (e.g. biopsies, surgical procedures, medical procedures) (see description of listing in Section 15.1.1).

### 15.2.4.3 Potential TGF- $\beta$ -mediated skin adverse events

To identify potential skin AEs possibly related to TGF- $\beta$  inhibition, MedDRA PT queries will be used to search for skin AEs of interest in the clinical database. A listing containing these pre-specified PT search terms will be generated. PTs will be compiled into categories: Narrow definition, and Broad definition:

**Narrow definition:**

- Keratoacanthoma
- Squamous cell carcinoma of skin

**Broad definition** has additional PTs:

- Hyperkeratosis
- Actinic keratosis
- Basal cell carcinoma
- Lip squamous cell carcinoma
- Bowen's disease

Further details (e.g. MedDRA PT queries) are regularly updated based on the current MedDRA version.

The overall summary of skin TEAE will include the following categories for narrow and broad definition:

- All skin TEAE
- All skin TEAE by worst grade
- Skin TEAE leading to permanent treatment discontinuation
- Serious skin TEAEs

Tables for skin TEAEs frequency will be provided by MedDRA PTs (including both narrow and broad definition PTs). A listing of skin AEs will also be provided, containing participant identifier, age, sex, race, first and last date of study intervention, preferred term, reported term for the AE, start date, end date, duration of AE (in days), day relative to the first infusion, day relative to the most recent infusion prior to AE onset, relationship to study treatment, toxicity grade, action(s) taken, outcome, seriousness (Y/N). Plus, from the "TGF $\beta$  Mediated Skin Reaction" eCRF page, the number of lesions, confirmation of the diagnosis (Y/N) and lesion location.

### 15.2.4.4 Anemia

A listing of anemia will be provided with the relevant information (see description of listing in Section 15.1.1).

The following high level terms (HLT) and PTs will be used to select the anemia AEs to be included in the listing:

- Anaemias NEC (HLT)
- Anaemias haemolytic immune (HLT)
- Anaemias haemolytic NEC (HLT)
- Haemoglobin decreased (PT)

## 15.3 Clinical Laboratory Evaluation

Baseline and on-treatment laboratory values (including corresponding normal ranges), converted in standard unit, will be used for summary statistics and shift tables.

Laboratory results will be classified according to the NCI-CTCAE criteria version 5.0 and as specified in [Appendix 3](#). Additional laboratory results that are not part of NCI-CTCAE will be categorized as follows: below normal limits, within normal limits, and above normal limits (according to the original laboratory normal ranges).

Quantitative data will be summarized using descriptive statistics (mean, standard deviation, median, Q1, Q3, minimum, and maximum) of actual baseline values, on-treatment values and changes from baseline to each on-treatment visit over time. Refer to Section 9 to the consideration of Unscheduled assessments. Qualitative data based on reference ranges will be described according to the categories (i.e. Abnormal, Normal).

Summary tables over time will present summary statistics for continuous and categorical variables by timepoint.

The following figures will be provided:

- Boxplots of the laboratory values by timepoint
- Boxplots of the change from baseline by timepoint

Boxplots for laboratory parameters where toxicity grades are defined based on the ratio of the parameter values and the upper limit of normal (ULN) will not be displayed using the unit of measurement but instead using the ratio of the measured value over ULN. This comprises alkaline phosphatase (ALP), alanine aminotransferase (ALT), aspartate aminotransferase (AST), Activated Partial Thromboplastin Time (aPTT), bilirubin, and creatinine.

### Laboratory parameters with NCI-CTC grades available

Laboratory parameters with NCI-CTC grades available will be analyzed with their respective NCI-CTC name and direction of abnormality. For parameters which are graded with both low and high values as potassium (hypokalemia/hyperkalemia), the toxicities will be summarized separately. Low direction toxicity (e.g. hypokalemia) grades at baseline and post-baseline will be set to 0 when the variables are derived for summarizing high direction toxicity (e.g. hyperkalemia), and vice versa.

The following summaries will be displayed:

- Number and percentage of participants by worst on-treatment grade ( $\geq 1$ ,  $\geq 3$ ,  $\geq 4$ )

- Shift in toxicity grading from baseline to highest on-treatment toxicity grade

The definitions of the NCI-CTCAE toxicity grading version 5.0 for each parameter are provided in [Appendix 3](#) of this IAP.

**Table 7** NCI-CTC Gradable parameters

Parameter	Parameter code	Name in NCI-CTC	Direction of abnormality
Biochemistry			
Alanine Aminotransferase	ALT	Alanine aminotransferase increased	High
Albumin	ALB	Hypoalbuminemia	Low
Alkaline Phosphatase	ALP	Alkaline phosphatase increased	High
Amylase	AMYLASE	Serum amylase increased	High
Aspartate Aminotransferase	AST	Aspartate aminotransferase increased	High
Bilirubin total	BILI	Blood bilirubin increased	High
Calcium a	CA	Hypercalcemia/Hypocalcemia a	High/Low
Creatinine	CREAT	Creatinine increased	High
Glucose	GLUC	Hypoglycemia	Low
Lipase	LIPASET	Lipase increased	High
Potassium	K	Hyperkalemia/Hypokalemia	High/Low
Sodium	SODIUM	Hypernatremia/Hyponatremia	High/Low
Hematology			
Absolute eosinophils	EOS	Eosinophilia	High
Absolute lymphocyte	LYM	Lymphocyte count decreased/Lymphocyte count increased	High/Low
Absolute neutrophils	NEUT	Neutrophil count decreased	Low
Hemoglobin	HGB	Anemia/Hemoglobin increased	Low/High
Leukocytes (WBC)	WBC	Leukocytosis/White blood cell decreased	High/Low
Platelets count	PLAT	Platelet count decreased	Low
Coagulation			
Activated Partial Thromboplastin Time b	APTT	Activated partial thromboplastin time prolonged	High
Activated PTT/Standard b	APTTSTND	Activated partial thromboplastin time prolonged	High
Prothrombin International Normalized Ratio b	INR	INR increased	High

a based on corrected calcium (see [Appendix 3](#))

b reported on the “Coagulation” eCRF page

For **WBC differential counts** (neutrophil, lymphocyte counts), the absolute value will be used when reported. When only percentages are available (this is mainly important for neutrophils and

lymphocytes, because the CTCAE grading is based on the absolute counts), the absolute value is derived as follows:

Derived differential absolute count = (WBC count) \* (Differential %value / 100)

For calcium, CTCAE grading is based on corrected calcium. Corrected calcium is calculated from albumin and calcium as follows based on the International System of Units (SI):

Corrected calcium (mmol/L) = measured total calcium (mmol/L) + 0.02 (40 – serum albumin [g/L]).

### **Laboratory parameters with NCI-CTC grades not available**

**Table 8** Non-NCI-CTC Gradable Parameters

Parameter (LBTEST)	
Biochemistry	
Bilirubin direct	BILIDIR
Bilirubin Indirect	BILINDIR
Chloride	CL
C-Reactive Protein	CRP
Total Protein	PROT
Urea Nitrogen	BUN
Hematology	
Absolute Basophils	BASO
Absolute Monocytes	MONO
Absolute Reticulocytes	RETI
Basophils/Leukocytes	BASOLE
Eosinophils/Leukocytes	EOSLE
Erythrocytes (RBC)	RBC
Hematocrit	HCT
Lymphocytes/Leukocytes	LYMLE
Mean Corpuscular Hemoglobin	MCH
Mean Corpuscular HGB Concentration	MCHC
Mean Corpuscular Volume	MCV
Monocytes/Leukocytes	MONOLE
Neutrophils/Leukocytes	NEUTLE
Reticulocytes/Erythrocytes	RETIRBC
Coagulation	
Prothrombin Time*	PT
Standard Prothrombin Time*	PTS

\* reported on the “Coagulation” eCRF page

For all non-gradable parameters, the following summaries will be displayed:

- Number and percentage of participants by lowest on-treatment value (classified as normal, high, low)

- Number and percentage of participants by highest on-treatment value (classified as normal, high, low)
- Shift from baseline to highest/lowest on-treatment value (classified as normal, high, low)

Separate listings of hematology, biochemistry and coagulation will be created. Each listing will include: participant identifier, age, sex, race, first dose date, last dose date, laboratory parameter (units), visit, date, International System of Units (SI) value, lower limit of normal (LLN), upper limit of normal (ULN), indicator of normal range (low, normal, high), toxicity grade according to NCI-CTCAE (when applicable) and highest/lowest on treatment value flag. Baseline and post-baseline values after the on-treatment period will be flagged. These listings will be sorted by participant identifier, parameter and laboratory measurement date.

### Liver function tests

Alanine aminotransferase (ALT), aspartate aminotransferase (AST), and total bilirubin are used to assess possible drug induced liver toxicity. The ratios of test result over upper limit of normal (ULN) will be calculated and classified for these three parameters during the on-treatment period.

The number and percentage of participants within each of the following liver function categories during on-treatment period will be described:

- ALT <3×ULN, ALT ≥ 3×ULN, ALT ≥ 5×ULN, ALT ≥ 10×ULN, ALT ≥ 20×ULN
- AST <3×ULN, AST ≥ 3×ULN, AST ≥ 5×ULN, AST ≥ 10×ULN, AST ≥ 20×ULN
- (ALT and AST) <3×ULN, (ALT or AST) ≥ 3×ULN, (ALT or AST) ≥ 5×ULN, (ALT or AST) ≥ 10×ULN, (ALT or AST) ≥ 20×ULN
- Total Bilirubin (TBILI) < 2×ULN, TBILI ≥ 2×ULN
- Concurrent ALT ≥ 3×ULN and TBILI ≥ 2×ULN
- Concurrent AST ≥ 3×ULN and TBILI ≥ 2×ULN
- Concurrent (ALT or AST) ≥ 3×ULN and TBILI ≥ 2×ULN
- Concurrent (ALT or AST) ≥ 3×ULN and TBILI ≥ 2×ULN and ALP > 2×ULN
- Concurrent (ALT or AST) ≥ 3×ULN and TBILI ≥ 2×ULN and ALP ≤ 2×ULN or missing

Concurrent measurements are those occurring on the same date.

Categories will be cumulative, i.e., a participant with an elevation of AST ≥10×ULN will also appear in the categories ≥5×ULN and ≥3×ULN.

A plot of peak ALT versus peak total bilirubin, both relative to the ULN will be provided. This eDISH plot (evaluation of drug-induced serious hepatotoxicity) will be divided into 4 quadrants by the lines through ALT ≥ 3×ULN and total bilirubin ≥2×ULN. The left lower quadrant is then considered normal or insignificant elevations in liver chemistries, the upper quadrants indicate

participants with possible Gilbert's cholestasis; the right upper quadrant are the possible Hy's Law participants; the right lower quadrant is possible Temple's Corollary (participants with  $ALT \geq 3 \times ULN$  but not satisfying Hy's Law). Same plot will be provided for AST.

In addition, a listing of all total bilirubin, ALT, AST and ALP values for participants with a post-baseline total bilirubin  $\geq 2 \times ULN$ ,  $ALT \geq 3 \times ULN$  or  $AST \geq 3 \times ULN$  will be provided.

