### **Type of Participant and Disease Characteristics**

2. Are participants with histologically or cytologically confirmed locally advanced or metastatic BTC.
3. Availability of tumor (primary or metastatic) archival material or fresh biopsies is mandatory. Fine needle aspirates, transductal aspirates, or cell blocks are not acceptable. Endoscopic retrograde cholangiography or intraductal ultrasounds assisted biopsy is acceptable, needle or excisional biopsies, or resected tissue, are preferable. Tumor biopsies and tumor archival material must be suitable for biomarker assessment as described in the Laboratory Manual.
4. Participants with BTC must have failed or be intolerant to 1L systemic platinum-based chemotherapy administered for locally advanced or metastatic disease. Only one prior treatment line is allowed. Participants who received adjuvant platinum-based chemotherapy and had evidence of disease recurrence within 6 months of completion of the adjuvant treatment are also eligible. If recurrence occurs during or within 6 months after the adjuvant chemotherapy, adjuvant platinum-based chemotherapy is counted as 1L chemotherapy.
5. Disease must be measurable with at least 1 unidimensionally measurable lesion by RECIST 1.1 and verified independently by IRC.
6. Eastern Cooperative Oncology Group (ECOG) PS of 0 to 1 at study entry and Day 1 of treatment with M7824.

7. Life expectancy  $\geq$  12 weeks as judged by the Investigator.
8. Adequate hematological function defined by white blood cell count  $\geq 3 \times 10^9/\text{L}$  with absolute neutrophil count  $\geq 1.5 \times 10^9/\text{L}$ , lymphocyte count  $\geq 0.5 \times 10^9/\text{L}$ , platelet count  $\geq 75 \times 10^9/\text{L}$ , and hemoglobin (Hgb)  $\geq 9 \text{ g/dL}$ .
9. Adequate hepatic function defined by a total bilirubin level  $\leq 1.5 \times$  upper limit of normal (ULN), an aspartate aminotransferase level  $\leq 2.5 \times$  ULN, and an alanine aminotransferase (ALT) level  $\leq 2.5 \times$  ULN. For participants with liver involvement in their tumor, aspartate aminotransferase  $\leq 5.0 \times$  ULN and ALT  $\leq 5.0 \times$  ULN is acceptable.

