### Definition of on-treatment period:

On-treatment period is defined as the time from the first study intervention to the last study intervention date + 30 days OR the earliest date of subsequent anticancer therapy minus 1 day, whichever occurs first, unless otherwise stated. For participants with treatment ongoing at cut-off date, all data from the first study intervention up to the cut-off date will be considered under the on-treatment period.

For immune-related AEs as listed in Section 15.2.4.2, an expanded on-treatment period will be used as a default for any analysis:

Time from the first study intervention to the last study intervention date + 90 days, death OR to the earliest date of subsequent anticancer therapy minus 1 day, whichever occurs first, unless otherwise stated.

Any systemic anticancer therapy, any anticancer surgery and any anticancer radiotherapy as documented in the "Anti-cancer treatment after discontinuation" CRF page will be considered as subsequent anticancer therapy.

The on-treatment period will include the initial treatment period as well as the reinitiation of treatment period, as applicable. Whether a participant reinitiates treatment (following the rules as outlined in the protocol) or not, the on-treatment period is defined as the time from the first study intervention administration to the last study intervention administration date + 30 days or the earliest date of subsequent anticancer drug (anticancer therapy, anticancer surgery and anticancer radiotherapy) therapy minus 1 day, whichever occurs first, unless otherwise stated.

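### The on-treatment liver categories and eDISH plots have no baseline reference, so an ALT or AST elevation present at entry can be counted at 3×ULN or more without any worsening

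*SAP*

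**What the plan says.** **Entry limits (Protocol Section 5.1, criterion 9).** The criterion opens "Adequate hepatic function defined by a total bilirubin level" and caps bilirubin at 1.5×ULN for everyone. AST and ALT are capped at 2.5×ULN, with one exception: "For participants with liver involvement in their tumor, aspartate aminotransferase" and ALT up to 5.0×ULN are acceptable.

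**Liver categories (SAP Section 15.3, Liver function tests).** For ALT, AST and total bilirubin, "The ratios of test result over upper limit of normal (ULN) will be calculated" and then classified. "The number and percentage of participants within each of the following liver function categories during on-treatment period will be described". The rows are ALT, AST, and either of them, at 3, 5, 10 and 20×ULN or more; bilirubin at 2×ULN or more; and same-date combinations of the two, the last pair split by ALP above or not above 2×ULN. No row carries a baseline condition.

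**eDISH plots (same section).** "A plot of peak ALT versus peak total bilirubin, both relative to the ULN will be provided", with dividing lines at 3×ULN for ALT and 2×ULN for bilirubin, and a matching plot for AST. In the SAP's labels, "the right upper quadrant are the possible" Hy's Law participants, and "the right lower quadrant is possible Temple's Corollary".

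**Time window (SAP Section 9).** "On-treatment period is defined as the time from the first study intervention to the last study intervention date + 30 days", or until the day before subsequent anticancer therapy if that is earlier. A pre-dose value is therefore not itself an on-treatment value. An elevation has to be present at a later draw to be counted.

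**The concern.** The SAP uses these displays to look for possible drug-induced liver toxicity. Immune-related hepatitis is an important identified risk for the drug (Protocol Sections 2.3 and 6.9.2). The trial has one arm, so no control group shows how often such values arise from the disease alone. The Protocol itself names obstructive cholestasis as a disease-specific risk (Section 6.9.6.3).

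The entry limit and the lowest transaminase threshold overlap: 5×ULN is allowed at entry for some participants, and counting starts at 3×ULN. In the table and plots, a participant whose ALT stays at 4×ULN throughout looks the same as one whose ALT rises from normal to 4×ULN. The first adds to the apparent signal, and the second is harder to see because of it.

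**Working it through.** The plan states no figure on this point, so there is none to reproduce. The check compares each entry cap with each threshold.

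**Inputs.** Entry caps come from Protocol Section 5.1, criterion 9. Thresholds come from SAP Section 15.3. N = 141 comes from Protocol Section 9.2.

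**Formula.** Fold rise needed from the cap = threshold ÷ entry cap. A result of 1 or less means that an eligible value can meet the category with no worsening.

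| Measure and group | Entry cap (×ULN) | Threshold (×ULN) | Fold rise needed |
|---|---|---|---|
| ALT/AST, liver involvement | 5.0 | 3 | 3/5.0 = 0.6 |
| | 5.0 | 5 | 5/5.0 = 1.0 |
| | 5.0 | 10 | 10/5.0 = 2.0 |
| | 5.0 | 20 | 20/5.0 = 4.0 |
| ALT/AST, no liver involvement | 2.5 | 3 | 3/2.5 = 1.2 |
| | 2.5 | 5 | 5/2.5 = 2.0 |
| | 2.5 | 10 | 10/2.5 = 4.0 |
| | 2.5 | 20 | 20/2.5 = 8.0 |
| Bilirubin, all | 1.5 | 2 | 2/1.5 = 1.33 |

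**Reachable with no worsening.** This applies only to participants with liver involvement. They can reach the 3×ULN rows, the 5×ULN rows if the entry value is exactly 5.0, and the lower right (possible Temple's Corollary) quadrant.

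**Not reachable from eligible entry values alone.** These are the 10 and 20×ULN rows, the bilirubin row at 2×ULN or more, every concurrent row, and the upper right (possible Hy's Law) quadrant.

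**Mixed case.** Take a participant with ALT unchanged at 4×ULN whose bilirubin goes from 1.5 to 2.0×ULN. On a common date this meets the concurrent ALT and bilirubin row, and it plots in the upper right quadrant. The transaminase condition was met at entry, so only the 1.33-fold bilirubin rise is new. The plot is slightly looser than the rows: it uses the two peaks, which need not fall on the same date.

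**Number affected.** The documents give no baseline ALT/AST distribution. Assume that a proportion p enters at 3 to 5×ULN and that the elevation persists to an on-treatment draw. The count is p × 141:

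- p = 2%: 0.02 × 141 = 2.8, about 3
- p = 5%: 0.05 × 141 = 7.1, about 7
- p = 10%: 0.10 × 141 = 14.1, about 14
- p = 20%: 0.20 × 141 = 28.2, about 28

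For context, Protocol Section 9.2 assumes 45% intrahepatic cholangiocarcinoma, or 0.45 × 141 = 63 participants. The group to which the higher cap could apply is therefore not small. How many of them enter above 3×ULN is unknown.

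**Caveat.** The caps are eligibility limits. The SAP baseline is the last non-missing value before the first dose, which may differ from the screening value.

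**The case against.** The strongest reply is that entry status is available elsewhere in the SAP. Section 15.3 plans shift tables from baseline grade to worst on-treatment grade, and Table 7 includes ALT, AST, ALP and bilirubin among the graded parameters. It plans change-from-baseline summaries and boxplots. It also lists all bilirubin, ALT, AST and ALP values for anyone crossing 3×ULN on a transaminase or 2×ULN on bilirubin after baseline. In a trial of this size, a reader can look up each flagged case. The ALP split within the concurrent rows helps to identify cholestasis.

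Much of this stands, and it rules out saying that liver safety as a whole ignores baseline. It does not close the gap. The shift tables and change summaries take one parameter at a time, so they cannot describe the combined rows or the quadrants. The ALP rows use on-treatment ALP without its baseline, criterion 9 sets no ALP limit, and the plots do not show ALP. The listing answers the question only case by case. The grading rules sit in a separate file (SAP Appendix 3), so any baseline adjustment there cannot be checked; the categories discussed here do not use grades.

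Three stronger readings are tempting, and the documents do not support them:

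- A reader might infer that entry elevations alone create Hy's Law cases, or that any bilirubin rise in this group does. The 1.5×ULN entry cap excludes the first. The 2×ULN threshold excludes the second.
- A reader might infer that immune-related hepatitis counts are inflated. SAP Section 15.2.4.2 identifies those events by a separate algorithm: preferred term, onset or worsening after the first dose, treatment given, and etiology or biopsy. Under Protocol Appendix 4, baseline conditions that do not worsen are not adverse events.
- A reader might infer that these values are declared to be hepatotoxicity. The SAP calls them possible cases and attaches no test or decision to them.

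**Conclusion.** The point holds for the liver-category table and the ALT and AST eDISH plots. The distortion of the ALT/AST counts at 3×ULN, and of the possible Temple's Corollary quadrant, is upward and arises in participants with liver involvement. For the concurrent rows and the possible Hy's Law quadrant the effect is indirect: a true bilirubin rise to 2×ULN is required, but the transaminase half of the definition may already have been met at entry.

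The range of about 3 to 28 of 141 is an illustration. It rests on an assumed 2% to 20% entering at 3 to 5×ULN and on every such elevation persisting. The true number could lie outside it. The matter is one of clear presentation of descriptive safety data, and it is a cheap improvement worth making.

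**What to change.** In the SAP Section 15.3 liver-category table, add a split by baseline: ALT and AST both below 3×ULN, versus either at or above 3×ULN. Use the baseline already defined in SAP Section 9. In the ALT and AST eDISH plots, use a different symbol for the two groups, or draw separate panels. For participants at or above 3×ULN at baseline, also show the peak on-treatment value as a multiple of baseline. Keep the ULN-based rows as they are, so that results stay comparable with other studies.

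The SAP already combines a threshold with a change from baseline for vital signs (Section 15.4), so the approach is not new to the document.

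The cost is one extra table section and a plotting symbol, from data already collected. The section for raised baseline values may hold few participants and should be read as description only.
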